NCT02676843

Study Title: Tau PET imaging with 18F-AV-1451 in subjects with MAPT mutations

IRB Protocol Number: AAAP4551

Version: 07/24/2015

Principal Investigator: [name]

Co-Investigator: [name]

Study Coordinator: [name]

PROTOCOL SUMMARY

Research question(s):

A novel PET tracer (18F-AV-1451) designed to measure the amount of tau protein in the brain will detect abnormal accumulations of tau in the brains of patients with tau mutations, but not their unaffected relatives.

Scientific abstract:

Objective: To determine the ability of a new PET tracer that binds to tau, 18F-AV-1451, to detect tau in subjects with and without mutations in the MAPT gene the codes for the protein tau.

Study Population: Control subjects without MAPT mutations, presymptomatic mutation carriers, and symptomatic mutation carriers.

Outcome measures:

The primary outcome measure will be a qualitative assessment of tau deposition on the 18FAV-1451 scans

Lay abstract:

We will be testing the ability of a new PET tracer, 18F-AV-1451, to detect depositions of a protein, called tau, in the brains of people with a mutation in the tau gene that causes deposition of the protein and in people without the mutation.

Subject Selection

Patients will be recruited from existing studies and from patients seen in the Columbia memory disorders clinic.

Inclusion criteria: Members of families with established MAPT mutations, who either have the capacity to consent to participate in the protocol, or else have designated a surrogate/proxy to consent to participate in this study.

Exclusion criteria: Unwillingness to participate and/or on a medication which significantly prolongs QT interval.

Safeguards for Vulnerable Populations

The proposed study, including the potential risks and benefits, will be discussed with the potential subjects, and they will be given copies of the consent form to read. Decision-making capacity to provide informed consent, including understanding the purpose of the study and the risks and benefits of participating, will be assessed by the evaluating physician and documented in the chart. Individuals with intact decision-making capacity will sign the consent form. We expect the majority of subjects to have capacity to provide informed consent.

All subjects with impaired capacity to provide informed consent will be evaluated by the physician for their ability to assign a surrogate. Subjects who demonstrate capacity to assign a surrogate will identify a surrogate for the remainder of the study. Surrogates permitted are

designated family members (only patient, spouse, or adult child), or may be another individual chosen by Patient Chosen Surrogate (PCS) method. The study will be explained to each potential subject and surrogate, and written informed consent must be obtained from the surrogate. If the participant does not have the capacity to assign a surrogate, he or she will not be allowed to participate in the study. The consent process will be repeated at each evaluation, and the above procedures will be followed for any individual that loses capacity during the course of the study. Subjects will not be given diagnoses as part of their participation in this protocol. Some may be symptomatic and have received a diagnosis and others may be presymptomatic and had genetic testing and know their status. This knowledge will not preclude their participation in the study, but diagnosis and genetic information will not be given to subjects through their participation in this study.

Study Purpose and Rationale

We will examine tau deposition in patients with MAPT mutations and their family members using a new PET tracer, 18F-AV-1451. MAPT mutations cause Frontotemporal dementia (FTD). We have an opportunity to examine the tau deposition in genetic FTD by obtaining 18F-AV-1451 tau tracer imaging on symptomatic, pre-symptomatic, and non-carrier subjects in families with MAPT mutations. This will achieve the following important aims: 1. Elucidate the early course of genetic FTD due to tau. When does tau start to be laid down? What are the earliest brain regions affected? 2. Validate the 18F-AV-1451 tau tracer by demonstrating its ability to distinguish MAPT mutation carriers from non-carriers.

Study Design and Statistical Procedures

This is an initial proof of concept study. As such, we will qualitatively examine each scan for tau positivity and not perform quantitative statistical analyses.

Study Procedures

We propose to perform 18F-AV-1451 scanning on 16 subjects from families with known tau mutations over 2 years (8 per year) including 6 controls, 5 presymptomatic mutation carriers, and 5 symptomatic mutation carriers. The controls will be non-mutation carrying members of families in which some family members have MAPT mutations. Pregnant women will be excluded from the study. The tracer will be manufactured at Avid Radiopharmaceuticals in Philadelphia, PA and transported to Columbia University Medical Center by courier for administration. See (Zhang et al., 2012) for details of 18F-AV-1451 synthesis and quality control. Adverse events will be monitored continuously during the imaging session. Subjects who experience any adverse event during an imaging session will not be discharged until the event has resolved or stabilized.

Study Drug

18F-AV-1451, also known as [18F] T807, is a tracer that was developed by Avid Radiopharmaceuticals, a company later acquired by Lilly, to image tau protein in humans in vivo. It has shown suitable tau affinity, target selectivity, and pharmacokinetic characteristics for tau imaging (see below) (Zhang et al., 2012). The developers of 18F-AV-1451 have reviewed the effects of the 10 +14 C>T mutation observed in our family and the mutation should not interfere with 18F-AV-1451 binding to tau in the 10 +14 C>T mutation carriers. We have successfully

applied to Avid radiopharmaceuticals for the use of 18F-AV-1451 and they have approved us to use 18F-AV-1451 for investigation and are providing us the tracer for free.

Autoradiography studies have demonstrated that 18F-AV-1451 binds with high affinity to tau positive brain sections from AD patients, whereas minimal to no binding was observed in tau negative, amyloid positive samples or in tau negative and amyloid negative control groups (Chien et al., 2013). The correlation of 18F-AV-1451 in these autoradiography studies was high ($r^2=0.9036$) for paired helical filament-tau (PHF-tau, the aggregated fibrillary form) and low for -amyloid ($r^2=0.0827$). The K_d calculated for 18F-AV-1451 binding to tau protein in human brain slices was measured to be approximately 15 nM. Subsequently, the K_d calculated for 18F-AV-1451 binding to PHF-tau purified from the human brain samples was measured at 0.7 nM. In vivo animal kinetic studies were supportive of further development as 18F-AV-1451 demonstrated rapid uptake in mouse, rat, and monkey brain followed by moderate clearance (Zhang et al., 2012; Chien et al., 2013). 18F-AV-1451 is being used for research purposes and will be handled in accordance with the CUMC Research Pharmacy procedures and NYP policy P168, Version 4. Effective date: August 24, 2009 34 Investigational Drugs: Use and Control.

Study Subjects

We propose to perform 18F-AV-1451 scanning on 16 subjects over 2 years (8 per year) including 6 controls, 5 presymptomatic mutation carriers, and 5 symptomatic mutation carriers.

Recruitment

Subjects who previously participated in a previous protocol at Columbia will be recruited for this study. These subjects already have an existing relationship with the PI. Subjects participating in that protocol who meet the inclusion, but not the exclusion, criteria of this study will be told about the study and given the contact information of this study team by [name].

Participants will also be recruited from patients seen at the Columbia Memory Disorders Clinic. The physicians at this clinic will be informed of this study so that if they identify a potential subject for this study, they can give that patient our contact information for potential participation in this study.

Informed Consent Process

We will obtain informed consent prior to any procedures. Only subjects with capacity to provide their own consent may consent or subjects who have a legally-authorized representative or guardian or a designated health care proxy that does not exclude research may consent on behalf of the subject to participate in this study. The study will be explained to each prospective patient or representative, and written informed consent must be obtained from the patient or representative before the patient participates in any study-related procedures.

Confidentiality of Study Data

Each participant's identity and participation in this study will be kept confidential in our database. All records will be stored in a computer file and access will be restricted to research staff. All questionnaires and other forms generated from the data collection will be kept in locked file cabinets, and only the investigators will have access to this information. Participant names will not be used. Rather, we will assign a code number that will be associated with all

information collected. Information presented or published for scientific purposes will not include participant names.

Privacy Protections

Research records are maintained in locked paper files and secured computer files, available only to research staff and institutional personnel as part of routine audits. Information is coded and password protected. Access is restricted to the authorized scientific investigators.

Identity of participants will not be shared with any investigators. Data that has been stripped of all identifying information from genetic analysis will be kept separate from the clinical and demographic data stored at the Taub Institute and can only be accessed by authorized individuals.

Potential Risks

Preclinical toxicity studies of 18F-AV-1451 (i.e. using non-radioactive 18F-AV-1451) showed a good safety profile with no observable effects at high multiples of the intended maximum human dose (Chien et al., 2013). The initial exploratory investigations of 18F-AV-1451 have been performed as part of two studies in older human subjects with a low probability of AD, in older subjects with a high probability of AD and in middle aged and young control subjects.

The objectives of the two studies were to establish the preliminary safety of 18F-AV-1451 and to assess the feasibility of 18F-AV-1451 as a potential PET biomarker for imaging pathological tau in human brains. As of the cutoff date of 19 September 2013, a total of 18 subjects have been enrolled in these studies (unpublished data from Avid Radiopharmaceuticals). Each subject received one intravenous bolus dose of approximately 10 mCi (370 MBq) of 18F-AV-1451. 18F-AV-1451 was well-tolerated; three subjects reported adverse events that were mild in severity and not considered related to study drug administration (two subjects reported headache, one subject reported diarrhea).

No consistent or clinically significant changes in vital signs, laboratory, and ECG values were observed in a completed analysis of 11 subjects. Preliminary human dosimetry results for 18F-AV-1451 have been computed for 3 subjects. The results showed both hepatobiliary and, to a smaller extent, renal excretion, and total effective dose similar to other approved F-18 radiopharmaceuticals. The organs of the gastrointestinal tract (upper large intestine, small intestine and liver) received the greatest exposure. The whole body effective dose for a 10 mCi (370 MBq) dose of 18F-AV-1451 was calculated to be 9.18 mSv (unpublished data from Avid Radiopharmaceuticals).

Data and Safety Monitoring

We will not have a specific Data and Safety Monitoring Board. Adverse events will be documented in the patient's chart. As far as possible, each adverse event will be described in the following manner and tabulated: 1) duration; 2) severity grade (i.e. mild, moderate, serious); 3) relationship to study; and 4) actions taken by the investigators. Unexpected and serious adverse events will be reported to the IRB within 2 days for death or life threatening events, and within 15 days for all others. We will also report all adverse events to Avid Radiopharmaceuticals who is monitoring safety data for this compound.

We will ensure proper monitoring per FDA and IRB guidelines, including ensuring that the study is conducted in accordance with the protocol. We will review all ongoing investigations of 18F-AV-1451 and give our evaluations of the safety and usefulness of this compound to the FDA and the IRB. We will keep all records per FDA and IRB guidelines and submit all amendments, IND safety reports and annual reports to the FDA and IRB.

Potential Benefits

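### The primary outcome is a qualitative scan read, and nothing in the protocol keeps the reader unaware of mutation or symptom status

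*Combined protocol and SAP*

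**What the plan says.** The Protocol Summary names one outcome: "The primary outcome measure will be a qualitative assessment of tau deposition on the 18FAV-1451 scans". Study Design and Statistical Procedures adds that "we will qualitatively examine each scan for tau positivity and not perform quantitative statistical analyses". No other tau outcome is listed.

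That outcome serves a contrast whose expected result is partly given in advance. Under Research question(s), the tracer "will detect abnormal accumulations of tau in the brains of patients with tau mutations, but not their unaffected relatives". The second aim in Study Purpose and Rationale is to "Validate the 18F-AV-1451 tau tracer by demonstrating its ability to distinguish MAPT mutation carriers from non-carriers". For presymptomatic carriers the expectation is less clear, because the first aim asks "When does tau start to be laid down".

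Study Procedures sets the sample at 16 subjects, "including 6 controls, 5 presymptomatic mutation carriers, and 5 symptomatic mutation carriers".

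The protocol does not say who reads the scans, how many readers there are, or what they may know about the subject. The nearest text concerns confidentiality. Confidentiality of Study Data says names will not be used and "we will assign a code number that will be associated with all" information collected. Privacy Protections says "Identity of participants will not be shared with any investigators" and that de-identified genetic data are stored apart from clinical data.

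**The concern.** In a validation study the group label is the standard against which the reads are judged. A reader who knows the label can supply the answer, most easily on equivocal scans. Part of any symptomatic-carrier versus control difference would then be prior knowledge, and the study could not separate that part from tracer performance. Since no quantitative measure is planned, nothing else in the plan could check the calls.

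Knowledge of group status is plausible here. The statistical section assigns the reading to the study team, and Recruitment says that subjects from the previous protocol already have a relationship with the principal investigator. Calls on presymptomatic carriers could also be affected, but the documents do not fix the direction: the second aim groups them with all carriers, while the research question could place them with unaffected relatives.

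**Working it through.** **1. Does any text mask the reader?** The protocol has no statement on blinding, masking or independent reading. The candidate passages are:

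| Text | What it protects | Does it mask the scan reader? |
|---|---|---|
| Code numbers (Confidentiality of Study Data) | Names | Not applied to scan reading; group status is not withheld |
| Identity rule (Privacy Protections) | Identity | Mutation and symptom status are not mentioned |
| Separate genetic data (Privacy Protections) | Stored genotype | May limit access to genotype; silent on symptoms and on the reader |
| Non-disclosure of diagnosis and genotype (Safeguards for Vulnerable Populations) | Subjects | Binds what subjects are told, not what readers know |

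**2. What one call is worth.** The group sizes are consistent (6 + 5 + 5 = 16 = 2 years × 8). One changed call moves:
- control positivity by 1/6 = 16.7 points;
- a carrier group of five by 1/5 = 20 points;
- all-carrier positivity by 1/10 = 10 points.

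**3. Illustration of expectation bias.** The protocol gives no error rate, effect size or success threshold, so there is no stated figure to reproduce. Every input below except the group sizes is an assumption:
- the tracer is uninformative;
- a fraction e of scans is equivocal;
- a share r of those is read toward the expected answer;
- all other scans are called positive at rate q;
- a gap of 50 points or more serves as the yardstick.

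Put d = e × r. Symptomatic carriers are called positive with probability d + (1 − d)q and controls with probability (1 − d)q, so the spurious gap is d. At e = 30%, r = 100%, q = 30% these are 0.30 + 0.70 × 0.30 = 51% and 0.70 × 0.30 = 21%, a gap of 30 points.

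All combinations of call counts were enumerated with exact binomial probabilities. For presymptomatic carriers three cases were run: pushed up like symptomatic carriers, not pushed, or read down like controls. At q = 30%, the chance of an observed gap of 50 points or more is:

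| e, r | Symptomatic (5) vs control (6) | All carriers (10) vs control (6): up / not pushed / down |
|---|---|---|
| no bias | 3.0% | 2.1% |
| 10%, 50% | 4.5% | 3.6% / 2.9% / 2.7% |
| 30%, 50% | 9.2% | 8.6% / 5.3% / 4.1% |
| 30%, 100% | 21.6% | 23.4% / 11.3% / 7.3% |

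In the last row the mean all-carrier gap is 30 / 19.5 / 15 points.

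**4. Sensitivity to q** (all carriers vs control, e = 30%, r = 100%). At q = 10% the chance rises from 0.1% to 20.1% / 3.3% / 2.2%. At q = 50% it rises from 2.9% to 22.5% / 14.9% / 8.9%.

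**5. A perfect split.** Bias alone rarely produces 10/10 versus 0/6. At e = 30%, r = 100%, q = 30% and presymptomatic scans pushed up, the chance is 0.51^10 × 0.79^6 = 0.03%.

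**The case against.** The strongest reply is that this argues from silence. The reader is not identified, masking may be set out in an imaging manual that is not part of these documents, and nothing shows the reads will be open. That is correct: what is established is a missing safeguard, not an unmasked read. The safeguard still belongs in the protocol, because the plan can be followed to the letter with group status known.

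Second, the identity rule combined with code numbers, taken literally, would leave an investigator-reader with no name to link to a chart. In practice it could limit knowledge of symptoms as well as genotype. This has some force, but coded data can still carry group status, some subjects are already known to the principal investigator, and neither rule is applied to the reads.

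Third, the calculation leans on assumed inputs and a worst-case premise, since the protocol cites evidence of tau affinity and selectivity. No test is planned, so no stated error rate is inflated. The per-call figures follow from small groups whether or not reads are masked. All of this stands. The figures show how fragile the contrast is and how far bias could move it; they do not estimate the actual bias, and mild bias has little effect.

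Fourth, this is a proof-of-concept study. That explains the absence of formal tests. It does not justify leaving the sole listed outcome unprotected when a stated aim is validation.

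**Conclusion.** The concern holds. The omission is certain from the text; the inflation is a possibility that the documents neither show nor exclude. The harm falls on the descriptive contrast and the validation claim.

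Its size depends on how many scans are equivocal and how strongly expectation steers them, and the protocol informs neither. Over the assumed range at q = 30%, the added chance of a spurious 50-point symptomatic-control gap runs from 4.5 − 3.0 = 1.5 to 21.6 − 3.0 = 18.6 percentage points. A complete separation of the groups would be hard to attribute to reader expectation alone. The exposure lies in intermediate results, where one or two equivocal calls decide the interpretation. The change should be made before any scan is read, because calls made with group status known cannot afterwards be turned into masked ones.

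**What to change.** Add to Outcome measures and to Study Design and Statistical Procedures that:
- scans are read from coded files, with carrier and control scans intermixed;
- the reader has no access to mutation status, symptom status or clinical notes;
- each call is recorded and locked before group status is revealed;
- the code numbers and the separation of genetic data already described under Confidentiality of Study Data and Privacy Protections apply to the reads.

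An existing team member who does not read scans can hold the key.

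The cost is two or three sentences and the coding of 16 image files. The amendment must also go to the FDA and IRB, as Data and Safety Monitoring already commits the study to do. With 8 subjects a year, formal reads must wait until enough scans of both kinds are available to intermix. Two limits remain: cues within the images cannot be masked, and masking does not supply a definition of a positive scan.

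### Aim 2 promises to validate the tracer, but the analysis plan rules out the statistics that would give such a claim an error rate or precision

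*Combined protocol and SAP*

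**What the plan says.** All of the relevant text is in the combined protocol and SAP.

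- *Study Purpose and Rationale* introduces two aims with the words "This will achieve the following important aims". The second is: "Validate the 18F-AV-1451 tau tracer by demonstrating its ability to distinguish MAPT mutation carriers from non-carriers".
- *Study Design and Statistical Procedures*, the next section, consists of two sentences: "This is an initial proof of concept study". "As such, we will qualitatively examine each scan for tau positivity and not perform quantitative statistical analyses".
- *Protocol Summary* states the research question as an expectation that the tracer "will detect abnormal accumulations of tau in the brains of patients with tau mutations, but not their unaffected relatives". Its outcome statement reads: "The primary outcome measure will be a qualitative assessment of tau deposition on the 18FAV-1451 scans".
- *Study Procedures* sets 16 subjects, "including 6 controls, 5 presymptomatic mutation carriers, and 5 symptomatic mutation carriers", and describes the control group: "The controls will be non-mutation carrying members of families in which some family members have MAPT mutations".

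No section gives a sensitivity, specificity, interval, group comparison or success criterion, and none gives a reason for the number 16.

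**The concern.** Proof-of-concept status is a good reason not to plan a powered test. It is not a reason to promise validation. To say that a tracer tells two groups apart is to say how often it is positive in one and negative in the other. The research question makes both claims: tau is seen in people with mutations and not in their unaffected relatives. The analysis section excludes the summaries that would express either claim.

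The excluded item could be read as image quantification and not statistics. Its wording, and its place under a heading on statistical procedures, favour the statistical meaning. On either reading no rate or interval is planned.

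What is at stake is the strength of the conclusion. Under *Potential Benefits* the protocol looks ahead to diagnosis and to a possible marker of treatment response. A statement that the tracer is validated, with no uncertainty attached, could be carried into those uses.

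The groups to be compared also matter. Aim 2 names carriers against non-carriers, while the research question speaks more loosely of patients and unaffected relatives. Presymptomatic carriers could fall on either side of that looser wording, so the results could look quite different depending on where they are counted.

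**Working it through.** **The plan's own figure.** 6 + 5 + 5 = 16, and 8 per year × 2 years = 16, so the count is consistent. It cannot be derived from a sample-size formula, because no alpha, power, expected rate or precision target is stated.

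**Inputs.** Carriers: 5 symptomatic + 5 presymptomatic = 10. Non-carriers: 6. All three group sizes come from *Study Procedures* and are repeated in *Study Subjects*. The 95% level and the independence of subjects are assumptions; the documents state neither.

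**Method.** Exact (Clopper-Pearson) limits suit groups this small. When all n reads agree with group status, the lower limit is 0.025^(1/n):

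- all carriers, 10/10: 0.025^(1/10) = 0.692
- symptomatic carriers, 5/5: 0.025^(1/5) = 0.478
- controls, 6/6 negative: 0.025^(1/6) = 0.541

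When one of n does not agree, the lower limit p solves n·p^(n−1)·(1−p) + p^n = 0.025:

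- 9/10: 10p⁹(1−p) + p¹⁰ = 0.025 gives p = 0.55498, or 55%
- 5/6: 6p⁵(1−p) + p⁶ = 0.025 gives p = 0.359, or 36%

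| Result | Estimate | Exact 95% interval |
|---|---|---|
| 10/10 carriers positive | 100% | 69% to 100% |
| 5/5 symptomatic carriers positive | 100% | 48% to 100% |
| 6/6 controls negative (specificity) | 100% | 54% to 100% |
| 9/10 carriers positive | 90% | 55% to 99.7% |
| 5/6 controls negative | 83% | 36% to 99.6% |
| 5/10 carriers positive (symptomatic only) | 50% | 19% to 81% |

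**Why the groups must be named beforehand.** Suppose the 5 symptomatic carriers are positive and everyone else is negative. The two-sided Fisher exact test then gives p = 0.093 for all carriers against controls (5/10 against 0/6) and p = 0.0022 for symptomatic carriers against controls (5/5 against 0/6). The same 16 scans read as weak or strong evidence according to the contrast chosen.

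**What a test alone would not show.** Perfect separation, 10/10 against 0/6, gives p = 1/8008 = 0.00012 (8008 is the number of ways to choose 6 from 16). That is evidence of a difference between the groups, if subjects are independent. It does not establish that either rate is high, because the lower limits remain 69% and 54%.

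**The case against.** The strongest defence is that the document calls itself a proof of concept, and that a descriptive reading of 16 scans is a reasonable design for one. The objective in the *Protocol Summary* is also milder than Aim 2, since it speaks only of determining the tracer's ability to detect tau. No decision or success threshold hangs on the verb, and because each scan is read in groups of known size, anyone could compute the proportions and intervals afterwards. All of this stands. It limits the defect to a mismatch between aim and analysis and shows that no data are lost. It does not give the validation claim any support in the plan.

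Four stronger readings are tempting, and the documents do not support them.

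- *The study is too small or needed a powered test.* No precision or power target is stated against which 16 could fail, and a proof of concept does not require one.
- *A negative scan in a presymptomatic carrier is a reading error.* Aim 1 asks when tau starts to accumulate, so such a carrier may have none yet. For that reason the carrier result is called positivity here. The contrast of 10 against 6 follows Aim 2, but it mixes tracer performance with timing of disease.
- *Adding intervals would settle the error rate.* The document does not define a positive scan or say how many readers there are or whether they are blind to carrier status. Exact intervals cover sampling error only.
- *A Fisher test would be safe, or conservative, because controls are relatives of carriers.* The protocol says that controls come from families with mutations. It does not say that they come from the same families as the enrolled carriers, or in what proportions.

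**Conclusion.** The concern holds as a mismatch that should be corrected. It is not a flaw that prevents the study from yielding useful descriptive data. Aim 2 is worded as validation, and the plan excludes any statistic that would attach an error rate or precision to it.

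Even the best possible outcome would leave carrier positivity as low as 69% and specificity as low as 54% compatible with the data, so the verb would overstate the result whatever the scans show. These limits rest on the planned group sizes, a 95% level and independent subjects. Because the subjects come from families, the intervals may be too narrow.

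**What to change.** Keep the visual read as the primary outcome and make two changes of wording.

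1. In *Study Design and Statistical Procedures*, replace the clause that excludes quantitative statistics with:

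   > Reads will be reported as positives/n for symptomatic carriers, presymptomatic carriers and controls, with exact (Clopper-Pearson) 95% intervals. The Aim 2 contrast is all carriers vs non-carriers (10 vs 6), with symptomatic carriers vs controls (5 vs 6) as a secondary description. The intervals treat relatives as independent, may be too narrow, and cover sampling error only, not error in the reads.

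2. In *Study Purpose and Rationale*, restate Aim 2 as:

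   > Obtain preliminary evidence that the tracer distinguishes MAPT mutation carriers from non-carriers.

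An exploratory Fisher exact test of the 10 vs 6 contrast is optional. If it is added, the text should say that it ignores family clustering and that the direction of its error depends on how families split across the groups. Where both groups draw evenly on the same families, a family effect moves both alike and the test tends to be conservative. Where they do not, a family effect can pass for a carrier effect and the test is too liberal.

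The cost is one paragraph and one small table, with no extra subjects, scans or readers. The downside is a little more analysis work, visibly wide intervals and a less favourable claim.
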